### **8.1.1. Baseline Procedures**

All procedures listed in the [SoA](#) must be conducted at this visit.

[SoA](#) must be conducted must be conducted at the screening visit.

### **8.2. Efficacy Assessments**

Not Applicable.

### **8.3. Safety Assessments**

Planned time points for all safety assessments are provided in the [SoA](#). Unscheduled safety measurements may be obtained at any time during the study to assess any perceived safety issues.

#### **8.3.1. Physical Examinations**

A complete physical examination will include, at a minimum, head, ears, eyes, nose, mouth, skin, heart and lung examinations, lymph nodes, and gastrointestinal, musculoskeletal, and neurological systems.

A brief physical examination will include, at a minimum, assessments of general appearance, the respiratory and cardiovascular systems, and participant-reported symptoms.

Physical examinations may be conducted by a physician, trained physician's assistant, or nurse practitioner as acceptable according to local regulation.

Height and weight will also be measured and recorded as per the [SoA](#). For measuring weight, a scale with appropriate range and resolution is used and must be placed on a stable, flat surface. Participants must remove shoes, bulky layers of clothing, and jackets so that only light clothing remains. They must also remove the contents of their pockets and remain still during measurement of weight.

Physical examination findings collected during the study will be considered source data and will not be required to be reported, unless otherwise noted. Any untoward physical examination findings that are identified during the active collection period and meet the definition of an AE or SAE ([Appendix 3](#)) must be reported according to the processes in [Sections 8.4.1 to 8.4.3](#).

### **8.3.2. Vital Signs**

#### **8.3.2.1. Blood Pressure and Pulse Rate**

Supine BP will be measured with the participant's arm supported at the level of the heart, and recorded to the nearest mm Hg after approximately 5 minutes of rest. The same arm (preferably the dominant arm) will be used throughout the study. Participants should be instructed not to speak during measurements.

The same properly sized and calibrated BP cuff will be used to measure BP each time. The use of an automated device for measuring BP and pulse rate is acceptable; however, when done manually, pulse rate will be measured in the brachial/radial artery for at least 30 seconds. When the timing of these measurements coincides with a blood collection, BP and pulse rate should be obtained prior to the nominal time of the blood collection.

Additional collection times, or changes to collection times, of BP and pulse rate will be permitted, as necessary, to ensure appropriate collection of safety data.

Any untoward vital sign findings that are identified during the active collection period and meet the definition of an AE or SAE ([Appendix 3](#)) must be reported according to the processes in [Sections 8.4.1 to 8.4.3](#).

#### **8.3.2.2. Temperature**

Temperature will be measured orally. No eating, drinking, or smoking is allowed for 15 minutes prior to the measurement.

### **8.3.3. Electrocardiograms**

Standard 12-lead ECGs utilizing limb leads (with a 10-second rhythm strip) should be collected at times specified in the [SoA](#) section of this protocol using an ECG machine that

automatically calculates the HR and measures PR interval, QT interval, QTcF, and QRS complex. Alternative lead placement methodology using torso leads (eg, Mason-Likar) should not be used given the potential risk of discrepancies with ECGs acquired using standard limb lead placement. All scheduled ECGs should be performed after the participant has rested quietly for at least 5 minutes in a supine position.

To ensure safety of the participants, a qualified individual at the investigator site will make comparisons to baseline measurements. Additional ECG monitoring will occur if a) a post-dose QTcF interval is increased by  $\geq 60$  ms from the baseline **and** is  $>450$  ms; or b) an absolute QT value is  $\geq 500$  ms for any scheduled ECG. If either of these conditions occurs, then 2 additional ECGs will be collected approximately 2 to 4 minutes apart to confirm the original measurement. If the QTcF values from these repeated ECGs remain above the threshold value, then a single ECG must be repeated at least hourly until QTc values from 2 successive ECGs fall below the threshold value that triggered the repeat measurement.

If a) a postdose QTcF interval remains  $\geq 60$  ms from the baseline **and** is  $>450$  ms; or b) an absolute QT value is  $\geq 500$  ms for any scheduled ECG for greater than 4 hours (or sooner, at the discretion of the investigator); or c) QTcF value get progressively longer, the participant should undergo continuous ECG monitoring. A cardiologist should be consulted if QTcF values do not return to less than the criteria listed above after 8 hours of monitoring (or sooner, at the discretion of the investigator).

In some cases, it may be appropriate to repeat abnormal ECGs to rule out improper lead placement as contributing to the ECG abnormality. It is important that leads be placed in the same positions each time in order to achieve precise ECG recordings. If a machine-read QTc value is prolonged, as defined above, repeat measurements may not be necessary if a qualified medical provider's interpretation determines that the QTcF values are in the acceptable range.

ECG values of potential clinical concern are listed in [Appendix 8](#).

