## 10.8. Appendix 8: ECG Findings of Potential Clinical Concern

ECG Findings That May Qualify as AEs

Marked sinus bradycardia (rate <40 bpm) lasting minutes.

New PR interval prolongation >280 ms.

New prolongation of QTcF to >480 ms (absolute) or by <math>\geq 60</math> ms from baseline.

New-onset atrial flutter or fibrillation, with controlled ventricular response rate: ie, rate <120 bpm.

New-onset type I second-degree (Wenckebach) AV block of >30 seconds' duration.

Frequent PVCs, triplets, or short intervals (<30 seconds) of consecutive ventricular complexes.

ECG Findings That May Qualify as SAEs

QTcF prolongation >500 ms.

New ST-T changes suggestive of myocardial ischemia.

New-onset LBBB (QRS complex >120 ms).

New-onset right bundle branch block (QRS complex >120 ms).

Symptomatic bradycardia.

Asystole:

In awake, symptom-free participants in sinus rhythm, with documented periods of asystole <math>\geq 3.0</math> seconds or any escape rate <40 bpm, or with an escape rhythm that is below the AV node.

In awake, symptom-free participants with atrial fibrillation and bradycardia with 1 or more pauses of at least 5 seconds or longer.

Atrial flutter or fibrillation, with rapid ventricular response rate: rapid = rate >120 bpm.

Sustained supraventricular tachycardia (rate >120 bpm) ("sustained" = short duration with relevant symptoms or lasting >1 minute).

Ventricular rhythms >30 seconds' duration, including idioventricular rhythm (HR <40 bpm), accelerated idioventricular rhythm (HR >40 bpm to <100 bpm), and

monomorphic/polymorphic ventricular tachycardia (HR >100 bpm [such as torsades de pointes]).

- Type II second-degree (Mobitz II) AV block.
- Complete (third-degree) heart block.

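### Minor: the absolute 500 ms ECG trigger in Protocol Section 8.3.3 is set in uncorrected QT for scheduled ECGs only, so it cannot operate after dosing

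*Protocol*

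**What the plan says.** Protocol Section 8.3.3 sets out an escalation path for a prolonged QT interval.

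- **Repeat-ECG trigger.** Limb (a) is a post-dose QTcF at least 60 ms above baseline and over 450 ms. The alternative begins "or b) an absolute QT value is" and, after the 500 ms figure, continues "ms for any scheduled ECG. If either of these conditions occurs, then 2 additional ECGs will be collected". Those two ECGs are taken about 2 to 4 minutes apart.
- **Confirmation and hourly repeats.** "If the QTcF values from these repeated ECGs remain above the threshold value, then a single ECG must be repeated at least hourly", and this goes on "until QTc values from 2 successive ECGs fall below the threshold value that triggered the repeat measurement".
- **Continuous-monitoring trigger.** Limb (a) is carried over. Limb (b) again names absolute QT of at least 500 ms, here "ms for any scheduled ECG for greater than 4 hours (or sooner, at the discretion of the investigator". Limb (c) is progressive lengthening of QTcF.
- **Referral.** "A cardiologist should be consulted if QTcF values do not return to less than the criteria listed above after 8 hours of monitoring".
- **Closing paragraph.** "If a machine-read QTc value is prolonged, as defined above, repeat measurements may not be necessary", where a qualified reader finds the QTcF acceptable.

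Section 8.3.3 takes its ECG times from the Schedule of Activities. In Table 1 the 12-lead ECG row is marked at Screening only. SAP Section 3.5.4 is consistent with that: the ECG baseline for every period is the latest screening measurement. Protocol Appendix 8 sets its own 500 ms limit in the corrected interval: "QTcF prolongation >500 ms".

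**The concern.** Limb (b) differs from the steps around it in two ways. It uses uncorrected QT, while limb (a), the confirmation step, limb (c), the referral and Appendix 8 all use QTcF. It also applies only to scheduled ECGs, and the study schedules none after the first dose.

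The second difference is the one that matters now. Any ECG after dosing is unscheduled, so the only absolute 500 ms trigger in the section cannot operate on treatment. A participant with a post-dose QTcF of 500 ms or more but a rise under 60 ms would not enter the mandatory sequence of two confirmatory ECGs followed by hourly repeats. Section 8.3.3 presents that sequence as a participant-safety measure, so its threshold should work on the ECGs that can actually occur after dosing.

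**Working it through.** The plan gives no figure to reproduce here. The check compares the texts and adds short arithmetic.

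**Inputs**
- Limbs (a) and (b), and the scheduled-only limit: Protocol Section 8.3.3.
- Scheduled ECGs: Table 1, Screening only.
- Rate correction: QTcF = QT / (60/HR)^(1/3), from SAP Section 3.5.4.
- Assumed for illustration: baseline QTcF of 440, 445 and 450 ms, and heart rates of 65 to 80 bpm. The documents give neither. Protocol Sections 5.1 and 5.2 require an ECG as part of the health assessment but set no numeric QTcF limit, so baselines above 440 ms are not excluded by number.

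**Step 1. What each limb can reach**

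| Limb | Metric | Screening ECG | Unscheduled post-dose ECG |
|---|---|---|---|
| (a) | QTcF rise of at least 60 ms, and over 450 ms | No (post-dose only) | Yes |
| (b) | QT of at least 500 ms | Yes | No (not scheduled) |

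**Step 2. The post-dose gap**

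Limb (a) first fires at baseline + 60 ms. In whole milliseconds, the uncovered QTcF values of 500 ms or more run from 500 to baseline + 59.

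| Baseline QTcF | Limb (a) fires from | Uncovered values | Count |
|---|---|---|---|
| 440 | 500 | none | 0 |
| 445 | 505 | 500–504 | 5 |
| 450 | 510 | 500–509 | 10 |

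At or below a baseline of 440 ms there is no gap. All of the uncovered values except 500 itself also exceed the Appendix 8 limit of 500 ms.

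**Step 3. Why both words must change**

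Take baseline 450 ms and an unscheduled post-dose QTcF of 505 ms at 80 bpm.

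- Rise: 505 − 450 = 55 ms, below 60, so limb (a) does not fire.
- Measured QT: 505 × (60/80)^(1/3) = 458.8 ms.

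| Wording of limb (b) | Fires? | Reason |
|---|---|---|
| As written | No | ECG not scheduled, and 459 is below 500 |
| QT changed to QTcF only | No | ECG not scheduled |
| Scheduled-only limit removed, nothing else | No | QT of 459 is below 500 |
| Both changed | Yes | QTcF of 505 is at least 500 |

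**Step 4. Where the QT/QTcF mismatch acts today**

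The two scales agree at 60 bpm. Above that rate, QTcF reaches 500 ms at a QT of 500 × (60/HR)^(1/3): 486.8 ms at 65 bpm, 475.0 at 70, 464.2 at 75 and 454.3 at 80. Under the present text, limb (b) reaches only the Screening ECG, so this mismatch is confined to people not yet dosed. It would extend to post-dose ECGs if the scheduled-only limit were removed on its own.

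**The case against.** The strongest reply is that this is a slip with almost no operation in the study. Several parts of that reply stand.

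- **Intended meaning.** The closing paragraph refers to a prolonged QTc as already defined, so absolute QT can be read as absolute, as opposed to change-from-baseline, QTcF. That reading is fair and would settle the metric. It does not remove the limit to scheduled ECGs.
- **Limb (a).** It uses QTcF, is not limited to scheduled ECGs, and already catches every post-dose value of 500 ms or more once the rise reaches 60 ms.
- **Other safeguards.** Appendix 8 lists a new QTcF above 480 ms as a possible AE, which covers the whole gap, and above 500 ms as a possible SAE. Protocol Section 8.4.3 and Appendix 3 require AE follow-up. Limb (c) covers progressive lengthening. Section 8.3.3 permits repeating an abnormal ECG, and Section 8.3 permits unscheduled measurements. None of these prescribes the two timed confirmations and the hourly series. Limb (c) does not cover a value that is prolonged but stable.
- **Likelihood.** About 12 healthy participants take single 30 mg doses. Protocol Section 2.3 reports no clinically significant ECG changes in earlier studies at much higher doses.

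A reader might infer that at 80 bpm a QTcF of 501–549 ms (QT 455–499 ms) goes unnoticed on treatment. The documents do not support that. As written, the band concerns only the Screening ECG, where the eligibility review in Sections 5.1 and 5.2 applies. After dosing, at a baseline of 450 ms, limb (a) fires from 510 ms.

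**Conclusion.** The wording is wrong as it stands, and the point is minor. The absolute 500 ms trigger cannot operate after dosing. The resulting gap is a QTcF of 500 ms or more with a rise under 60 ms on an unscheduled ECG, which is possible only if baseline QTcF exceeds 440 ms. It spans 5 ms at baseline 445 and 10 ms at baseline 450. What is lost is the mandatory timing of repeats, not all follow-up.

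This rests on a literal reading of the scheduled-only limit and on Table 1 showing the ECG at Screening only, which SAP Section 3.5.4 supports. Confidence is high for the wording; the practical effect is very small.

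Two stronger inferences should be resisted. Post-dose ECGs are not left without any trigger, because limb (a) still works on them. No result is at risk either: SAP Section 6.6.4 only holds ECG data in the database for request, and the pharmacokinetic analyses do not use the rule.

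**What to change.** In both the repeat-ECG and the continuous-monitoring sentences of Protocol Section 8.3.3, change limb (b) to: *an absolute QTcF value is ≥500 ms for any ECG (scheduled or unscheduled)*. Make both changes together, for the reason shown in Step 3.

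Changing QTc to QTcF in the stop step and in the closing paragraph is optional and editorial, since QTcF is the only correction the section names.

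The cost is one phrase in two places. No scheduled ECG, sample or analysis is added, and the ECG machine specified in Section 8.3.3 already reports QTcF.

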#### 8.3.4. Clinical Safety Laboratory Assessments

See [Appendix 2](#) for the list of clinical safety laboratory tests to be performed and the **SoA** for the timing and frequency. All protocol required laboratory assessments, as defined in [Appendix 2](#), must be conducted in accordance with the laboratory manual and the **SoA**. Unscheduled clinical laboratory measurements may be obtained at any time during the study to assess any perceived safety issues.

The investigator must review the laboratory report, document this review, and record any clinically significant changes occurring during the study in the AE section of the CRF. Clinically significant abnormal laboratory test findings are those that are not associated with the underlying disease, unless judged by the investigator to be more severe than expected for the participant's condition.

All laboratory tests with values considered clinically significant and abnormal during participation in the study or within 28 days after the last dose of study intervention should be

repeated until the values return to normal or baseline or are no longer considered clinically significant by the investigator or study medical monitor.

If such values do not return to normal/baseline within a period of time judged reasonable by the investigator, the etiology should be identified and the sponsor notified.

See [Appendix 6](#) for suggested actions and follow-up assessments in the event of potential DILI.

See [Appendix 7](#) for instructions for laboratory testing to monitor kidney function and reporting laboratory test abnormalities.

Participants may undergo random urine drug testing at the discretion of the investigator. Drug testing conducted prior to dosing must be negative for participants to receive study intervention.

### **8.3.5. COVID-19 Specific Assessments**

Participants will be tested for COVID-19 infection by PCR prior to being admitted to the clinic for confinement and a subsequent COVID-19 test will be performed after 4 days (ie, upon completion of 4 × 24 hours in house), or if they develop COVID-19-like symptoms. Additional testing may be required by local regulations or by the PI.

### **8.3.6. Pregnancy Testing**

A serum pregnancy test is required at screening. Following screening, pregnancy tests may be urine or serum tests, and must have a sensitivity of at least 25 mIU/mL. Pregnancy tests will be performed in WOCBP at the times listed in the [SoA](#). Following a negative pregnancy test result at screening, appropriate contraception must be commenced, and a second negative pregnancy test result will be required at the baseline visit prior to the participant's receiving the study intervention. Pregnancy tests will also be done whenever 1 menstrual cycle is missed during the active treatment period (or when potential pregnancy is otherwise suspected). Pregnancy tests may also be repeated if requested by IRBs/ECs or if required by local regulations.

## **8.4. Adverse Events, Serious Adverse Events, and Other Safety Reporting**

The definitions of an AE and an SAE can be found in [Appendix 3](#).

AEs may arise from symptoms or other complaints reported to the investigator by the participant (or, when appropriate, by a caregiver, surrogate, or the participant's legally authorized representative), or they may arise from clinical findings of the investigator or other healthcare providers (clinical signs, test results, etc).

The investigator and any qualified designees are responsible for detecting, documenting, and recording events that meet the definition of an AE or SAE and remain responsible to pursue and obtain adequate information both to determine the outcome and to assess whether the

event meets the criteria for classification as an SAE or caused the participant to discontinue the study intervention (see [Section 7.1](#)).

During the active collection period as described in Section 8.4.1, each participant will be questioned about the occurrence of AEs in a nonleading manner.

In addition, the investigator may be requested by Pfizer Safety to obtain specific follow-up information in an expedited fashion.

#### **8.4.1. Time Period and Frequency for Collecting AE and SAE Information**

The time period for actively eliciting and collecting AEs and SAEs (“active collection period”) for each participant begins from the time the participant provides informed consent, which is obtained before undergoing any study-related procedure and/or receiving study intervention), through and including a minimum of 28 calendar days, except as indicated below, after the last administration of the study intervention.

Follow-up by the investigator continues throughout the active collection period and until the AE or SAE or its sequelae resolve or stabilize at a level acceptable to the investigator.

When a clinically important AE remains ongoing at the end of the active collection period, follow-up by the investigator continues until the AE or SAE or its sequelae resolve or stabilize at a level acceptable to the investigator and Pfizer concurs with that assessment.

For participants who are screen failures, the active collection period ends when screen failure status is determined.

If the participant withdraws from the study and also withdraws consent for the collection of future information, the active collection period ends when consent is withdrawn.

If a participant permanently discontinues or temporarily discontinues study intervention because of an AE or SAE, the AE or SAE must be recorded on the CRF and the SAE reported using the CT SAE Report Form.

Investigators are not obligated to actively seek information on AEs or SAEs after the participant has concluded study participation. However, if the investigator learns of any SAE, including a death, at any time after a participant has completed the study, and they consider the event to be reasonably related to the study intervention, the investigator must promptly report the SAE to Pfizer using the CT SAE Report Form.

##### **8.4.1.1. Reporting SAEs to Pfizer Safety**

All SAEs occurring in a participant during the active collection period as described in Section 8.4.1 are reported to Pfizer Safety on the CT SAE Report Form immediately upon awareness and under no circumstance should this exceed 24 hours, as indicated in [Appendix 3](#). The investigator will submit any updated SAE data to the sponsor within 24 hours of its being available.

#### **8.4.1.2. Recording Nonserious AEs and SAEs on the CRF**

All nonserious AEs and SAEs occurring in a participant during the active collection period, which begins after obtaining informed consent as described in [Section 8.4.1](#), will be recorded on the AE section of the CRF.

The investigator is to record on the CRF all directly observed and all spontaneously reported AEs and SAEs reported by the participant.

As part of ongoing safety reviews conducted by the sponsor, any nonserious AE that is determined by the sponsor to be serious will be reported by the sponsor as an SAE. To assist in the determination of case seriousness, further information may be requested from the investigator to provide clarity and understanding of the event in the context of the clinical study.

#### **8.4.2. Method of Detecting AEs and SAEs**

The method of recording, evaluating, and assessing causality of AEs and SAEs and the procedures for completing and transmitting SAE reports are provided in [Appendix 3](#).

Care will be taken not to introduce bias when detecting AEs and/or SAEs. Open-ended and nonleading verbal questioning of the participant is the preferred method to inquire about AE occurrences.

#### **8.4.3. Follow-Up of AEs and SAEs**

After the initial AE or SAE report, the investigator is required to proactively follow each participant at subsequent visits/contacts. For each event, the investigator must pursue and obtain adequate information until resolution, stabilization, the event is otherwise explained, or the participant is lost to follow-up (as defined in [Section 7.3](#)).

In general, follow-up information will include a description of the event in sufficient detail to allow for a complete medical assessment of the case and independent determination of possible causality. Any information relevant to the event, such as concomitant medications and illnesses, must be provided. In the case of a participant death, a summary of available autopsy findings must be submitted as soon as possible to Pfizer Safety.

Further information on follow-up procedures is provided in [Appendix 3](#).

